
Research Summary

State your primary study objectives

Developmental (R21) Phase. We will develop and refine the FBI intervention in 26 child-caregiver dyads.

A1. Create a developmentally sensitive interoceptive exposure treatment for young children with FAP.

A2. Assess the initial feasibility of FBI.

Hypotheses: $HA2_a$, $\geq 80\%$ of participants enrolled in FBI will complete treatment, $HA2_b$, $\geq 80\%$ of participants will complete home-based practice assignments.

A3. Assess the clinical significance of FBI post-treatment.

Hypothesis : $HA3$, Children will endorse weekly pain and distress ratings of minimal to none (≤ 2).

Pilot-Test (R33) Phase. We will randomize 100 children with FAP to FBI or an active control (parent education with standard medical care).

B1. Determine feasibility of the intervention.

Hypotheses: $HB1_a$, $\geq 80\%$ of participants will complete treatment and $HB1_b$, homework.

B2. Determine the acceptability of the intervention.

Hypotheses: **HB2_a**, ≥ 80% of parents and children in FBI will endorse Very Much/Extreme positive ratings on treatment credibility and **HB2_b**, satisfaction.

B3. Assess clinically meaningful change in the intervention group compared to control.

Hypotheses: **HB3_a**, Compared to control, children in FBI will endorse: fewer episodes of abdominal pain (Faces Scale), **HB3_b**, greater reductions in impairment (Children's Global Assessment Scale)

State your secondary study objectives

Exploratory: greater improvements in emotion awareness and regulation via increased abilities to **HB3_c**, discriminate emotion from pain (via daily diaries) and **HB3_d**, regulate emotional experience (laboratory mood induction task).

Please select your research summary form:

Standard Research Summary Template

This is the regular (generic) research summary template which is required for all regular applications (unless your protocol fits under the other research summary templates in this category). Use of these instructions is helpful for ensuring that the research summary contains all necessary elements.

Standard Research Summary

Purpose of the Study

- Objectives & hypotheses to be tested

Developmental (R21) Phase. We will develop and refine the FBI intervention in 26 child-caregiver dyads.

A1. Create a developmentally sensitive interoceptive exposure treatment for young children with FAP.

A2. Assess the initial feasibility of FBI.

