Hypotheses: **HA2_a**, ≥ 80% of participants enrolled in FBI will complete treatment, **HA2_b**, ≥ 80% of participants will complete home-based practice assignments.

A3. Assess the clinical significance of FBI post-treatment.

Hypothesis : **HA3**, Children will endorse weekly pain and distress ratings of minimal to none (≤ 2).

Pilot-Test (R33) Phase. We will randomize 100 children with FAP to FBI or an active control (parent education with standard medical care).

B1. Determine feasibility of the intervention.

Hypotheses: **HB1_a**, ≥ 80% of participants will complete treatment and **HB1_b**, homework.

B2. Determine the acceptability of the intervention.

Hypotheses: **HB2_a**, ≥ 80% of parents and children in FBI will endorse Very Much/Extreme positive ratings on treatment credibility and **HB2_b**, satisfaction.

B3. Assess clinically meaningful change in the intervention group compared to control.

Hypotheses: **HB3_a**, Compared to control, children in FBI will endorse: fewer episodes of abdominal pain (Faces Scale), **HB3_b**, greater reductions in impairment (Children's Global Assessment Scale), and, **Exploratory:** greater improvements in emotion awareness and regulation via increased abilities to **HB3_c**, discriminate emotion from pain (via daily diaries) and **HB3_d**, regulate emotional experience (laboratory mood induction task).

Background & Significance

- Should support the scientific aims of the research

The Duke Tummy Pain (DTP) Study Research Summary

R-21 Phase

The Feelings and Body Investigators (FBI): Interoceptive Exposure for Child Abdominal Pain proposes to develop (R21) an acceptance-based behavioral treatment intervention for children 5 through 9 years old with impairing functional abdominal pain. Functional abdominal pain (FAP) is a frequent somatic complaint in young children (approximately 10% of those presenting to primary care) and is responsible for distress in the afflicted child and the family; unnecessary health care utilization and cost; and interference with schooling. Further, FAP is predictive of future pain disorders, psychiatric disorders, and impairment. Despite this prevalent and significant burden, there are currently no accepted successful treatments for FAP in young children.

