The objective of this proposal is to develop an intervention for FAP based on fundamental research on aberrant neurodevelopment of the gut-brain axis and subsequent modification by the social environment. In brief, this work suggests that FAP results from the influence of pain on the neurodevelopment of the gut-brain axis. The gut-brain axis maintains the body's homeostasis, encompassing capacities to sense changes in the viscera and respond adaptively (e.g., responding to gut pangs of hunger). Healthy maturation of the gut-brain axis is crucial for the emergence of weight and emotion regulation. Further, the interpretation of visceral signals has a developmental course, as children learn how to identify, label, and describe body sensations; e.g., whether gut sensations are butterflies of anxiety or gut pain. FAP represents a disruption of this normal developmental course. FAP may also be exacerbated by environmental influences (e.g., extensive medical diagnostic testing) that increase parents' health anxiety and their children's fear and distrust of their bodies. We propose to intervene directly early in development on these aberrations in gut-brain maturation by training eligible child-caregiver dyads to be feelings and body (FBI) investigators using interoceptive exposure (the manipulation of visceral sensation) to explore a "body mystery" in a playful, investigative context designed to increase curiosity about body function. Sessions are conducted in clinic and home (via web-camera) to facilitate generalization.

Because of limited sample size and the iterative nature of intervention development, criteria for success at the R21 Phase are based primarily on clinical rather than statistical criteria. We have established goals for compliance, completion, and reduction in physical and psychological distress aimed at establishing the feasibility and efficacy of the intervention. We carefully considered statistical constraints of pilot investigations by framing outcomes based on clinical but not statistical significance.

There are no known physical risks to the child or parent associated with this proposed study. There are minimal risks such as feeling uncomfortable answering questions.

Design & Procedures

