Pain: Children and their caregivers will be trained to complete pain ratings using a Daily Pain Diary which contains a Pain Thermometer to rate pain experienced and the Self-Assessment Manikin (SAM) scale to rate emotional experience. Caregivers are trained to use the child's verbal reports, facial expressions, and behaviors to make these ratings. Children make their ratings twice daily: in the morning and before dinner. Parents rate their child's pain three times daily: in the morning, before dinner, and at the end of the day. The end of day survey contains additional questions asking about the child's overall pain experience throughout the entire day, as well as their distress and mood. These ratings are completed for one week prior to treatment and one week post-treatment, on a daily basis. Pain ratings are collected during 2 of the 10 weeks of treatment.

Impairment: Change in function will be assessed by diagnostic interviews and global ratings of clinical and functional change by reviewers blind to the randomization on the basis of these interviews, functional status as reported in pain/emotion diaries, and medical chart review of frequency of visits and physician contacts.

Diagnostic Interviews: [name] is the leading author of the Preschool Age Psychiatric Assessment (PAPA), one of the most widely used and reliable semi-structured interviews for diagnosis of young child psychopathology. The caregiver reports on his or her child's family context, psychiatric diagnosis, self-regulatory abilities including sensitivity to sensation, developmental history, and impairment. Numerous studies have established its predictive validity and sensitivity to change with intervention. Impairment is assessed across multiple domains as well as the perceived cause of impairment (e.g. due to physical symptoms). To shorten administration, modules chosen are based on frequency of somatic symptoms and include ADHD, somatization, social phobia, separation anxiety, generalized anxiety, and depression.

Functioning ratings in daily pain diaries – Parents are asked to provide an assessment of their child's functioning three times per day. In the morning (beginning of day) and afternoon (before dinner), they rate their child's ability to pay attention and have fun whilst experiencing tummy pain. At the end of the day, they provide a detailed report of their child's physical and emotional functioning over the course of the day.

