As of February 2016, we have completed the R-21 phase of The Feeling and Body Investigators (FBI) Study (N=26) and have received approval to continue into the R-33 phase of the study. We are currently in the process of analyzing the data collected during the R-21 phase of the study, updating materials based on subject feedback, and preparing to begin recruitment of our next 100 subjects (N=100).

The R-33 phase, called The Duke Tummy Pain (DTP) Study, will differ from the R-21 phase in that we will be comparing our Investigational Treatment (Feeling and Body Investigator Treatment, or FBI) to a control treatment (Caregivers in Action Treatment, or CIA). Recruitment, eligibility criteria, and assessment strategies will stay the same as they were in the R-21 phase. Subjects recruited into the R-33 phase will be randomized to either the experimental treatment (FBI) or the control treatment (CIA), but both groups will receive the same number of treatment sessions (10), with 8 sessions conducted in our lab space and 2 sessions conducted via Skype.

The R33 period will repeat the goals of the R21 period using an improved intervention, a large sample to discern statistical and clinical significance, and a randomized design with a parent-psychoeducation comparison condition. Endpoints include quantification of whether this intervention can have broad impact: using primary care practices to screen and subsequently treat abdominal pain early in the life and disorder cycle.

Those who receive the FBI Investigational Treatment will still be trained using an improved version of the FBI R-21's interoceptive exposure (the manipulation of visceral sensation) to explore "body mysteries" in a playful, investigative context, designed to increase curiosity about body functions. The CIA (treatment as usual) focuses more on the parent, who will receive a psychoeducation comparison condition. Parents will receive educational handouts, similar to what they would receive from a Pediatricians office, and the therapist will review these materials with the parent, while the child is playing in the room.

As of November 2016, [name] (a Co-PI on this study) has taken a position at NYU and will no longer be working with subject's PHI for this study. [name] will now be moved to our "Outside Duke Key Personnel" and is still involved with Duke, but as an adjunct professor.

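### HA3 judges the clinical significance of FBI in the single-arm R21 phase by a fixed post-treatment cut of 2, so a child already at 2 or lower who does not change counts as meeting it

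*Protocol*

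**What the plan says.** **The aim and its criterion.** The protocol's Purpose of the Study section gives the aim as "A3. Assess the clinical significance of FBI post-treatment". The single hypothesis under it, HA3, is "Children will endorse weekly pain and distress ratings of minimal to none (≤ 2". No change from baseline, required share of children, or rule for turning a week of ratings into one number is given.

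**The design.** R21 has one arm: "We will develop and refine the FBI intervention in 26 child-caregiver dyads". The R-33 Phase section says that phase "will differ from the R-21 phase in that we will be comparing our Investigational Treatment" with a control, so the comparator belongs to R33 only.

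**The stated goal.** Background & Significance, R-21 Phase, says that "criteria for success at the R21 Phase are based primarily on clinical rather than statistical criteria". It then lists among the goals a "reduction in physical and psychological distress aimed at establishing the feasibility and efficacy of the intervention".

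**The available data.** On the pain diaries, Assessment Measures says: "These ratings are completed for one week prior to treatment and one week post-treatment, on a daily basis".

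**The analysis text.** Data Analysis & Statistical Considerations lists general methods and ties none of them to HA3. The SAP covers treatment completion and homework only.

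**The concern.** The goal is a reduction, but the criterion is a level. HA3 has one input, the post-treatment rating, and compares it with 2. Where the child started plays no part, although the pre-treatment diary week is collected.

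This matters because functional abdominal pain can be intermittent. A child can be impaired on a few bad days and still have a low weekly average: pain of 6 on 2 of 7 days averages 12/7 = 1.7. The documents as available describe entrants as having pain that causes impairment, but show no minimum diary rating for entry. Some children may therefore satisfy HA3 before the first session.

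At stake is the R21 statement on clinical significance. Read together with the efficacy wording in the background section, a high HA3 proportion could credit FBI with low pain that was already there or that came with the natural course.

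**Working it through.** The documents give no figure for HA3 to reproduce: no null value, required proportion, SD or expected rate. What can be checked is how the rule behaves when treatment does nothing.

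**Inputs from the documents:** cut of 2; 7-day diary weeks before and after treatment; 26 children; one arm.

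**Assumptions, not in the documents:** a 0-10 scale; pain-free days score 0; pain only unless stated; no treatment effect.

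**Check 1: fixed intensity.** Pain has level L on a share q of independent days.

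- 7-day mean: kL/7 ≤ 2, so a child passes if the number of pain days k ≤ 14/L (rounded down): k ≤ 3, 2, 1 for L = 4, 6, 8, with k ~ Binomial(7, q).
- Every day ≤ 2: a child passes only with no pain days, probability (1 − q)^7.

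For L = 6, q = 0.30: 0.7^7 + 7(0.3)(0.7^6) + 21(0.3²)(0.7^5) = 0.082 + 0.247 + 0.318 = 0.647. The strict reading gives 0.7^7 = 0.082.

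| q | Mean ≤ 2, L=4 | L=6 | L=8 | Every day ≤ 2 |
|---|---|---|---|---|
| 0.15 | 99% | 93% | 72% | 32% |
| 0.30 | 87% | 65% | 33% | 8% |
| 0.45 | 61% | 32% | 10% | 1.5% |
| 0.60 | 29% | 10% | 2% | 0.2% |

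At q = 0.80 the mean reading passes 3% or fewer.

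**Check 2: children differ.** Each child's pain-day probability is drawn from a beta distribution with mean d/7 and concentration 5. Intensity on pain days is normal with mean 5 and SD 2, clipped to 1-10. Simulated pass rates with no effect:

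| Pain days a week (d) | 7-day mean ≤ 2 | Every day ≤ 2 |
|---|---|---|
| 2 | 70% | 24% |
| 3 | 49% | 10% |
| 4 | 29% | 4% |

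Over d = 1 to 5 and mean intensity 3 to 7, the 7-day-mean rate runs from 96% down to 7%. Requiring distress ≤ 2 as well takes the 70% to about 65-67%. If HA3 instead means that the average of the 26 children is ≤ 2, it is met for pain 98% of the time at d = 2 and about 29% at d = 3.

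**Check 3: which use of the baseline week helps.** Same model, d = 2, 7-day mean, no effect. Before treatment 30% of children are above 2, about 0.30 × 26 = 8. Of these, 44% are at 2 or lower afterwards, and their mean change is about −0.8. That is regression to the mean. The full cross-table is:

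| | After ≤ 2 | After > 2 |
|---|---|---|
| Before ≤ 2 | 0.70 − 0.13 = 57% | 13% |
| Before > 2 | 0.30 × 0.44 = 13% | 0.30 − 0.13 = 17% |

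Of the 70% who pass, 57 points were already there. The two off-diagonal cells balance, and the mean paired change over all children is zero. Paired change in everyone is therefore not distorted in this model, whereas restricting to those above 2 is.

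**The case against.** The best defence is that R21 is developmental. The protocol says its success criteria are mainly clinical, and an end state of little or no pain is a recognisable clinical target. No decision rule or required proportion hangs on HA3. R21 also lists blind-rated Clinical Global Impression and Children's Global Assessment Scale ratings among its clinical-significance measures, so HA3 need not be the only evidence bearing on A3. The phase was complete by February 2016, and redefining its hypothesis afterwards would be improper.

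Most of this stands, and it limits the weight of the point. It does not explain why a goal worded as a reduction is judged by a rule that ignores the starting value. The other measures do not enter HA3's wording.

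Three stronger readings are tempting, and the documents do not support them.

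- *The weakness carries into R33.* The R-33 Phase section says "The R33 period will repeat the goals of the R21 period using an improved intervention", which might suggest that HA3 is reused. The same sentence adds randomisation and a comparison condition, and the R33 hypotheses HB3_a and HB3_b are worded against control. HA3 is not among them.
- *Most children would pass untreated.* That follows only from a 7-day mean and infrequent pain. If every day must be 2 or lower, or if pain is near daily, few pass.
- *Restricting to children above 2 at baseline cures the problem.* Check 3 shows that it introduces regression to the mean and leaves few evaluable children.

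**Conclusion.** The point holds for the R21 criterion. HA3 is an absolute post-treatment level in a single arm. It does not measure the reduction that the protocol names as its goal, and a child already at 2 or lower and unchanged counts as meeting it. Nothing in the statistical methods or the SAP corrects this.

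The size is unknown. The figures of about 70% (7-day mean) and 24% (every day) at 2 pain days a week and mean intensity 5 rest on an assumed scale, pain pattern and weekly summary. They show how far the answer depends on matters the plan leaves open and do not estimate what happened in R21. A reader might infer a false claim of efficacy. The documents support only that HA3 cannot distinguish benefit from low pain at the start or from natural course. The R33 comparison is unaffected.

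**What to change.** Leave HA3 as stated and keep the post-treatment proportion as a description. Add the following as a supplementary analysis of the existing R21 diaries, labelled as such because enrolment is complete:

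1. State the scale, whose rating is used (child or parent), and how a week is summarised.
2. Make the paired pre-to-post change in weekly pain, and separately in distress, the main A3 analysis, in all R21 children with diaries, with a 95% CI.
3. Give the before/after cross-table of 2 or lower against above 2, so that children already at 2 or lower are visible and are not counted as improved.
4. If a proportion is given among those above 2 before treatment, label it as subject to regression to the mean.
5. In Background & Significance, R-21 Phase, replace the efficacy wording with a statement that the single-arm result describes change and does not separate treatment from natural course. Paired change has this limit too: if families joined when symptoms were worse than usual, some improvement would occur untreated.

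The cost is a short re-analysis of data already collected, a wording change, and probably a less favourable-looking R21 result.
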